# 9.1.4.3 DEX Dose Modifications

Table 8 and Table 9 outline the dose reduction steps for DEX, and instructions for dose interruptions and reductions can be found in Table 10.

Table 8DEX Dose Reduction Steps (Less Than or Equal to 75 Years Old)

Dose Level	DEX Dose (Days 1, 8, 15, 22 of 28 days)
Starting Dose	40 mg
Dose Level -1	20 mg
Dose Level -2	10 mg ¹

1 DEX should be discontinued if subject is unable to tolerate 10 mg dose. Subjects may continue on single agent POM or LEN until disease progression.

Table 9DEX Dose Reduction Steps (More Than 75 years Old)

Dose Level	DEX Dose (Days 1, 8, 15, 22 of 28 days)
Starting Dose	20 mg
Dose Level -1	12 mg
Dose Level -2	$8 mg^1$

¹ DEX should be discontinued if subject is unable to tolerate 8 mg dose. Subjects may continue on single agent POM or LEN until disease progression.

Toxicity	DEX Dose Modification
Dyspepsia = Grade 1-2	Maintain dose and treat with histamine (H2) blockers or equivalent. Decrease by one dose level if symptoms persist.
Dyspepsia ≥ Grade 3	Hold dose until symptoms are controlled. Add histamine (H2) blocker or equivalent and decrease one dose level when dose is restarted.
Edema ≥ Grade 3	Use diuretics as needed and decrease dose by one dose level.
Confusion or mood alteration $\geq$ Grade 2	Hold dose until symptoms resolve. When dose is restarted decrease dose by one dose level.
Muscle weakness (steroid myopathy) $\geq$ Grade 2	Hold dose until muscle weakness $\leq$ Grade 1. When dose is restarted decrease dose by one dose level.
Hyperglycemia ≥ Grade 3	Decrease dose by one dose level. Treat with insulin or oral hypoglycemic agents as needed.
Acute pancreatitis	Discontinue subject from DEX treatment regimen.
Other $\geq$ Grade 3 dexamethasone-related adverse events	Stop DEX dosing until the adverse event resolves to $\leq$ Grade 2. Decrease by one dose level when DEX dosing is resumed.

Table 10	Dose Reductions for Dexamethasone Related Toxicities

DEX: dexamethasone

If recovery from toxicities is prolonged beyond 14 days, then the dose of DEX will be decreased by one dose level.

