Following completion of Parts D and E (dose escalation of MOR03087 in combination with POM+DEX and LEN+DEX), the MTD and/or recommended dose in each part will be confirmed in a minimum of 6 subjects.

All cohorts:

After the first administration of study drug, the subjects will remain at the site until the end of Day 2 for safety monitoring. The subjects will not stay overnight at the site for subsequent administrations.

Based on the individual risk/benefit ratio, subjects who have an ongoing response of at least stable disease (SD) may continue treatment with the assigned study regimen until disease progression or until a maximum of 3 years after first treatment. In case subjects present with progressive disease or with no better status than SD after four treatment cycles starting with Cycle 1 Day 1, the investigator may add a low weekly dose of DEX to the regimen at his/her discretion, provided DEX is not already part of the treatment regimen.

At least 3 subjects meeting all inclusion and none of the exclusion criteria, as determined at the screening visit (see Sections 8.1 and 8.2) will be enrolled into each cohort.

Enrolment into a cohort at the next higher dose level will be based on the data generated from the previous dose level and guided by clinical review until

- the maximum planned dose has been reached, or
- the review of the safety data indicates a need to either expand the current dose level cohort to include 6 subjects or stop the dose escalation or the study, or
- the review of Part B dose level 6b and Part C dose level 6c, including available safety information from Part A dose level 8, indicates that only some of the planned weekly MOR03087 monotherapy dose escalation cohorts should be tested.

The DMC safety review will take place after the third subject enrolled into a cohort has undergone minimum safety evaluations (as defined for the "DLT Evaluable Population" in Section 15.1). The safety assessment will take into account AEs reported from Day 1 after the start of the first infusion through Day 29 before the start of the second cycle. The next cohort will only be started after the positive outcome of the safety assessment.

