#### Table 5LEN Dose Modification Instructions for Toxicities

Toxicity	LEN Dose Modification
Neutropenia (ANC < 0.5 x 10 ⁹ /L)	Stop LEN dosing and follow hematology weekly. If the subject was not receiving GCSF therapy, GCSF therapy may be started at the discretion of the treating physician. When ANC returns to $\geq 0.5 \times 10^{9}$ /L, LEN dosing may be restarted at same dose level if neutropenia was the only DLT and GCSF treatments are continued, or decreased by one dose level. Note: GCSF is prohibited during Cycle 1
Thrombocytopenia (Platelets <30 x10 ⁹ /L)	Stop LEN dosing and follow hematology weekly. When platelets return to $\geq 30 \times 10^9$ /L, resume LEN dosing at one dose level lower

Toxicity	LEN Dose Modification
Rash	
 
Grade 2-3 skin rash: LEN interruption or discontinuation should be considered at the discretion of the treating physician.
 
Angioedema, Grade 4 rash, exfoliative or bullous rash or if Stevens-Johnson syndrome (SJS) or toxic epidermal necrolysis is suspected, LEN must be discontinued permanently
 

Other $\geq$ Grade 3 LEN-related adverse events	Stop LEN dosing and restart at one dose level lower when toxicity has resolved to $\leq$ Grade 2 at physician's discretion.

ANC: absolute neutrophil count; DLT: dose limiting toxicity; GCSF: granulocyte colony-stimulating factor; LEN: lenalidomide

LEN should be discontinued if the subject is unable to tolerate the lowest dose level. At the discretion of the investigator, the treatment with MOR03087 and dexamethasone may be continued.

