#### **10.1.13 Treatment Cycles 3+ Visits**

Subjects with an ongoing response of at least SD subsequent to the end of cycle 2 will be offered continued treatment with MOR03087 until disease progression or death or start of new anti-myeloma treatment.

At the discretion of the investigator, subjects with disease progression or a status no better than stable disease after four cycles may be treated with up to 40 mg DEX (elderly subjects aged > 75 years should receive 20 mg) per week if not otherwise receiving DEX via assigned cohort. Only subjects who do not present with known or suspected hypersensitivity to DEX or any of the excipients could qualify for the treatment with DEX (see exclusion criterion for the concomitant treatment of MOR03087 and DEX, Section 8.2). DEX must be administered as a single oral dose.

In case subjects are treated with DEX in the course of the study, the investigator may decide to decrease the dose of DEX when medically justified in the light of signs and symptoms resulting from the excess of glucocorticosteroids. The investigator must then adhere to the rules of local medical practice and their clinical judgment in the process, ensuring that subject treatment is stable (down-titration completed) prior to the End of Study (EOS) visit.

In case a subject discontinues treatment for reasons other than disease progression, they should proceed to the Follow-up Visit.

All subjects (females as well as males) continuing in the LEN and POM parts will receive an educational leaflet appropriate to their treatment, and will receive Pregnancy Counselling (see Section 12.2 and Appendix 18.8.1.3 / 18.8.2.3) at Day 1 of each cycle, starting with Cycle 3+.

At each ongoing treatment visit, the following will be obtained, performed, or assessed prior to study drug administration:

- Toxicity/AE assessment since the last visit
- Concomitant medication
- Karnofsky performance status only at Day 1 (CxD1) of each cycle, starting with Cycle 3+
- Laboratory assessments according to local guidelines/practice for the administration of monoclonal antibodies at the local laboratory should be performed. The assessment at the local laboratory should contain at the minimum serum chemistry including the "emergency laboratory parameters" and calcium concentration, and hematology
- Urine pregnancy test for women of child-bearing potential only at Day 1 (CxD1) of each cycle, starting with Cycle 3+

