	Percentage of actual dose vs. planned dose [%]	Total actual dose taken [mg]/ Planned dose [mg] Where planned dose = sum of (starting dose of each cycle * 21 days), calculated over all cycles initiated. Starting dose of each cycle is taken from eCRF POM administration page for Day 1 of each cycle
	Number of days with missed doses	Sum of durations of intake of zero dose [=Start date – Stop date + 1] over all entries (in the eCRF POM administration log) with reason other than “Subject is in Rest Period between Day22 and Day28”
	Any dose reduction	Any reduced dose (compared to starting dose in first cycle)
	Any permanent	Discontinuation of POM but continuation of

	discontinuation of POM but continuation of MOR03087	MOR03087 during at least 2 MOR03087 infusions until last MOR03087 dosing day
Exposure to Dexamethasone		
Variables calculated on a per-subject basis including data of all cycles	Number of applications	Number of DEX intakes where a study drug administration page is filled and the question “Was dexamethasone taken?” is answered with “Yes”.
	Total actual dose taken [mg]	Sum over all doses administered
	Average actual dose taken during days treated [mg]	Total actual dose taken [mg]/ number of intakes
	Number of infusion days without administration of DEX	Number of all MOR03087 infusions where a study drug administration page is filled out and it is not ticked “Infusion not given” but DEX is not taken
	Any dose reduction	Any reduced dose (compared to starting dose in first cycle)
	Any permanent discontinuation of DEX but continuation of MOR03087	Discontinuation of DEX but continuation of MOR03087 during at least 2 MOR03087 infusions until last MOR03087 dosing day

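### The DEX dose-reduction footnotes (Protocol Tables 8 and 9) let subjects who stop DEX continue on POM or LEN as a single agent; read literally this leaves out MOR03087, which the continuation rules and the SAP do not.

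*Protocol*

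**What the plan says.** Protocol Section 9.1.4.3 gives two DEX reduction ladders. The footnote for subjects aged 75 or younger says "DEX should be discontinued if subject is unable to tolerate 10 mg dose"; the one for older subjects says "DEX should be discontinued if subject is unable to tolerate 8 mg dose". Both then add: "Subjects may continue on single agent POM or LEN until disease progression". Neither mentions MOR03087.

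Other places bear on the same situation:

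- **Protocol 9.1.4.1 (LEN):** if the lowest LEN dose is not tolerated, LEN stops and "At the discretion of the investigator, the treatment with MOR03087 and dexamethasone may be continued". Section 9.1.4.2 has the same provision for POM.
- **Protocol 10.1.13 (Cycles 3+):** subjects with at least SD after Cycle 2 are offered "continued treatment with MOR03087 until disease progression or death or start of new anti-myeloma treatment".
- **Protocol 7.1 (all cohorts):** subjects with at least SD "may continue treatment with the assigned study regimen until disease progression or until a maximum of 3 years after first treatment".
- **SAP 7.3.6, Table 5 (dexamethasone):** a per-subject variable is defined as "Any permanent discontinuation of DEX but continuation of MOR03087".
- **Protocol 8.6:** if treatment is delayed by more than 14 days after a missed dose, it is to be permanently discontinued and the subject goes to the first follow-up visit.

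**The concern.** Every subject in Parts D and E is assigned MOR03087 plus DEX plus POM or LEN. If DEX is removed and the subject continues on POM or LEN as a single agent, the ordinary meaning is that MOR03087 has gone too. Elsewhere in the protocol MOR03087 is the component that stays when a partner drug is dropped, and the SAP is built on that pattern.

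Two things are at stake. First, whether a subject keeps receiving the drug under test may depend on how a site reads a footnote. Second, the SAP has no rule for the state that the literal reading creates. Response and progression-free time observed without MOR03087 could then enter the results for the triple combination.

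**Working it through.** No figure in the plan depends on this point, so the check sets the passages side by side and then counts who could be affected.

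**Step 1: what happens to MOR03087 when a partner drug stops**

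| Event | Source | What may continue |
|---|---|---|
| LEN stopped | Protocol 9.1.4.1 | MOR03087 + DEX |
| POM stopped | Protocol 9.1.4.2 | MOR03087 + DEX |
| DEX stopped at lowest step | Protocol 9.1.4.3, Tables 8 and 9 | POM or LEN as single agent |
| SD or better after Cycle 2 | Protocol 10.1.13 | MOR03087 |
| SD or better, all cohorts | Protocol 7.1 | Assigned regimen, 3-year maximum |
| DEX stopped (analysis variable) | SAP 7.3.6, Table 5 | MOR03087 |

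The DEX footnote is the only row that names what continues and leaves MOR03087 out. It also omits the 3-year limit in Section 7.1, although Section 10.1.13 omits it as well, so that part is minor. For all three partner drugs, SAP Table 5 defines only the case where the partner stops and MOR03087 continues. It has no variable for POM or LEN continuing after MOR03087 stops.

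**Step 2: where the sentence cannot apply**

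Part C is MOR03087 + DEX, with no POM or LEN. Subjects in cohorts without DEX who have it added after four cycles (Protocol 7.1 and 10.1.13) also receive neither. For both groups only the general rules in 7.1 and 10.1.13 remain, and neither addresses permanent DEX discontinuation. Table 10 gives a further route to stopping DEX (acute pancreatitis), also without saying what happens to the other study drugs.

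**Step 3: how the SAP would treat POM-only or LEN-only time**

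- The protocol synopsis lists POM and LEN among the investigational drugs. Continuing one of them is therefore not non-study MM treatment.
- SAP 7.3.3 disregards tumour assessments only after non-study anti-MM treatment starts, and Tables 2 and 3 censor DoR, TTP and PFS on the same trigger. Neither rule is activated.
- Duration of treatment (SAP Table 5) runs to the last dose of any IMP, so this time is counted as treatment.
- EFS (SAP 7.3.3.3) counts treatment discontinuation for any reason as an event, but does not say whether stopping MOR03087 alone qualifies.

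**Step 4: ceiling on the number affected**

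Inputs are the maximum numbers in the protocol synopsis: Part D 18, Part E 18, total 126.

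- POM-only or LEN-only time is possible only in Parts D and E: 18 + 18 = 36.
- 36 / 126 = 0.286, or 29% of the maximum enrolment.

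This counts subjects to whom the sentence could apply. It does not forecast how many will stop DEX, for which the documents give no rate. For scale, the smallest recommended-dose group is 9 (Protocol 15.9; SAP Section 5), so one subject is 1 / 9 = 11% of such a group.

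**The case against.** The strongest reply is that the footnote never stops MOR03087. It is permissive, and it sits in a section whose title covers only POM, LEN and DEX. The protocol's rules for postponing or stopping MOR03087 are elsewhere (DLTs, laboratory limits, delays, grade 3 or 4 infusion reactions), and DEX intolerance is not among them. With Section 10.1.13, a site has a basis for continuing MOR03087. The LEN and POM rules concern a different event, and the SAP variable describes exposure and does not instruct treatment. This stands in part: the footnote is open to two readings and collides with no other explicit rule on what follows a DEX stop. But nothing in the protocol chooses between the readings.

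On the analysis, SAP Table 5 reports infusions given and not given per subject, so missing MOR03087 would be visible. Section 8.6, if it applies to MOR03087 alone, may limit any long POM-only or LEN-only period. The endpoints concerned are secondary and descriptive, and MTD determination rests on Cycle 1. Not censoring when one component stops is also an accepted choice, and the SAP makes it when LEN or POM stops. These arguments reduce the consequence. They do not remove it, because exposure counts do not alter response or PFS, and the retained drug here would not be the one under test.

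A reader might infer three stronger claims. The documents do not support them:

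- **That the protocol orders MOR03087 to be stopped.** It does not say so.
- **That Part C has no applicable rule.** The instruction to stop DEX works there, and Sections 7.1 and 10.1.13 still cover continuation in general terms.
- **That all 60 subjects in Parts C, D and E (24 + 18 + 18) are exposed to the attribution problem.** Part C has no POM or LEN to continue on.

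**Conclusion.** The point holds as an internal inconsistency in a treatment instruction, with a limited consequence for analysis. The literal wording leaves out MOR03087 and does not fit the continuation rules, the parallel LEN and POM rules, or the SAP variable. It allows two readings that lead to different treatment.

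The attribution problem is conditional. It arises only if a Part D or E subject stops DEX and the site follows the literal reading so that MOR03087 also stops. It is further limited if Section 8.6 ends treatment after the delay. The ceiling is 36 of 126 subjects, and the actual number cannot be estimated from the documents. The results at risk are the secondary response, DoR, TTP and PFS summaries for Parts D and E, not the MTD. This review takes no position on which continuation rule is clinically right.

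**What to change.** **Protocol.** The sponsor should reconcile the footnotes to Tables 8 and 9 with Sections 7.1, 8.6, 9.1.4.1, 9.1.4.2 and 10.1.13 and with SAP Table 5. One consistent statement should cover what happens to each remaining study drug when DEX is permanently stopped, separately for Part C, Part D, Part E and subjects with DEX added later. It should also say whether the 14-day rule in Section 8.6 applies to MOR03087 alone.

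**SAP.** Add a sentence stating how tumour assessments made after MOR03087 has stopped, while POM or LEN continues, are analysed or flagged for response, DoR, TTP and PFS, and whether stopping MOR03087 alone is an EFS event. If that state remains possible, add a matching exposure variable to Table 5.

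The cost is footnote wording and a sentence or two in the SAP, plus one derived variable if needed. No new data collection appears to be required, since the SAP already draws on recorded MOR03087 infusions and LEN and POM administration logs.

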# 9.2 Method of Numbering Subjects and Assigning Subjects to Treatment Groups

Part A dose levels 1-7 will be tested sequentially and only one dose level will be open for enrolment at any time. Starting with Part A dose level 8, Parts B and C will open in parallel (at dose level 6 [6b and 6c]). Following completion of dose level 7c (8.0 mg/kg MOR03087 + DEX) (and dose level 7b if the DMC recommends to open this cohort), Cohorts 7d and 7e may open in parallel with dose levels 8b (if the DMC recommends to open this cohort) and 8c (see Section 7.1, Figure 1). New cohorts will not start before the DMC returns a positive recommendation based on safety read-outs from prior cohorts as laid down in the DMC Charter.

The allocation to a cohort will be technically managed by the IWRS system based on an external algorithm starting from cohorts 7c and 8.

For each subject screened, the investigator or designee will log into the IWRS system and will enter the month and year of birth and the gender. The IWRS will allocate the next available screening identification (ID) number, ensuring that screening ID numbers are assigned sequentially per site. The screening ID number will be a 5-digit number with the first 2 digits identifying the site (10, 11, ...) and the last 3 digits identifying the sequence number assigned

by the IWRS (001, 002, ...) for each site continuously. For sites located in Germany, the site number will start with 1 or 2, and for sites located in Austria with 3. Leading zeros will be used for the second part of the ID number to ensure a consistent length of 5 digits. The third subject screened at site 14 in Germany would, for example, be identified as 14003. The fourth subject screened at site 14 in Germany would, for example, be identified as 14004.

The investigator will enter the information (i.e., gender, month and year of birth and the associated screening ID number) into the confidential subject identification list.

If the subject qualifies, enrolment will be done centrally at baseline, again employing the IWRS. The part and dose level assignment has to be triggered via IWRS between 3 days and at least 16 hours before the planned administration of MOR03087. The fact that a subject has been enrolled will be reported immediately and automatically by the system to the dedicated pharmacist (if applicable), the investigator, the Clinical Research Organization (CRO), and the sponsor. The IWRS report will contain the information on the respective part/dose level the subject is enrolled to.

The IWRS will only allow enrolment to the next cohort with a higher dosing regimen in the respective study arm after that cohort has been actively opened in the IWRS system for enrolment following DMC review.

The subject will be identified by the previously assigned screening ID number throughout the study. No additional subject or randomization number will be used.

A subject enrolled in the study is not permitted to re-enroll for a second course of study participation.

Subjects who are considered screening failures may be re-screened again only once. In this case, the subjects will receive a new subject number. The period between both screening visits needs to be at least 6 weeks.

# 9.3 Blinding

Blinding at the level of study treatment does not apply since the study will be open label.

# 9.4 **Prior and Concomitant Therapy**

Any prior, concomitant, or procedural medications or therapy given to or taken by the subject within 1 month before and up to the end of the study will be recorded in the eCRF along with the indication and dosage. However, information should be provided on any previous myeloma-specific therapies since the time point of the first diagnosis of MM. This information should include start and end of administration, best response achieved using respective medication(s) with corresponding date and diagnosis of disease progression (date and type) using respective medication(s). The generic or the trade name may be recorded. Other than the IMP, subjects should not receive any other myeloma-specific therapy during the study.

Non-investigational medications needed to treat concomitant medical conditions may be continued during the study. Any other medication for treatment of symptoms of MM or concurrent diseases is allowed and can be prescribed at the discretion of the investigator.

However, the medical monitor should be contacted to discuss the use of any myeloma-related therapies before those therapies are started.

Subjects will continue to receive packed red blood cell (RBC) as clinically indicated. Information regarding transfusions during the study will be recorded in the eCRF.

Prophylactic treatment of thromboembolism for subjects enrolled into the LEN or POM parts of the study is mandatory. Low-dose aspirin, low molecular weight heparin, or other equivalent antithrombotic or anti-coagulant will be given during the study to all subjects assigned to receive POM or LEN. As of Day 29 (Cycle 2), GCSF therapy can be given at the discretion of the investigator, if clinically indicated.

However, treatments that might potentially interfere with the IMPs should be avoided and, with the exception of treatments required in emergency situations, these should be approved by the medical monitor prior to administration.

The investigator should instruct the subject not to take any additional medications (including over-the-counter-products) during the study without prior consultation. All medications (including over-the-counter medications) administered after the subject has signed the informed consent must be listed on the concomitant medications form in the eCRF.

All respective treatments, including for example transfusions, should be recorded in the eCRF as concomitant medication.

